11 SOURCE DOCUMENTS AND ACCESS TO SOURCE DATA/DOCUMENTS

If necessary and if appointed, the medical experts, study monitors, auditors, and health authority inspectors (or their agents) will be given direct access to source data and documentation (e.g., medical charts/records, laboratory test

results, printouts, videotapes) for source data verification, provided that patient confidentiality is maintained in accordance with local requirements.

Each Investigator must maintain, at all times, the primary records (i.e., source documents) of each patient's data. Examples of source documents are hospital records, office visit records; examining physician's finding or notes, consultant's written opinion or notes, laboratory reports, drug inventory, study drug label records, and CRFs that are used as the source.

Each Investigator will maintain a confidential patient identification list that allows the unambiguous identification of each patient. All study-related documents must be kept for a minimum of 5 years.

12 QUALITY ASSURANCE AND QUALITY CONTROL

Protocol Amendments: No changes from the final approved (signed) protocol will be initiated without the prior written approval or favorable opinion of a written amendment by the IEC/IRB, except when necessary to eliminate immediate safety concerns to the patients or when the change involves only logistics or administration. Each Investigator will sign the protocol amendment.

The IRB/EC may provide expedited review and approval/favorable opinion for minor change(s) in ongoing studies.

Protocol Deviations, Violations, and Exceptions: A **protocol deviation** is non-adherence to protocol-specific study procedures or schedules that does not involve inclusion/exclusion criteria, primary objective variable criteria, and/or GCP guidelines. Deviations are considered minor and do not impact the study.

A **protocol violation** is any significant divergence from the protocol, i.e., non-adherence on the part of the patient, the Investigator, or the sponsor to protocol-specific inclusion/exclusion criteria, primary objective variable criteria, and/or GCP guidelines. Protocol violations will be identified and recorded, by study center personnel.

No **exceptions** to protocol-specific entry criteria will be granted to allow patients to enter a study.

Information to Study Personnel: Each Investigator is responsible for giving information about the study to all staff members involved in the study or in any element of patient management, both before starting the practical performance of the study and during the course of the study (e.g., when new staff become involved). Each Investigator must assure that all study staff members are qualified by education, experience, and training to perform their specific responsibilities. These study staff members must be listed on the study center authorization form, (if required) which includes a clear description of each staff member's responsibilities. This list must be updated throughout the study, as necessary.

The PI is responsible for explaining the protocol to all study staff, including each Investigator, and for ensuring their compliance with the protocol. Additional information will be made available during the study when new staff become involved in the study and as otherwise agreed upon with either the Investigator or the study monitor.

The handling of data, including data quality assurance, will comply with regulatory guidelines (e.g., ICH and GCP) and the sponsor's or its designee's SOPs and working instructions. Data management and control processes specific to this study will be described in a data management plan. When data management is outsourced, the contract organization will be responsible for the development and implementation of the data management plan.

Data Quality Assurance: All data on the CRF will be entered into a validated database compliant with 21 CFR Part 11 requirements. In the case when data management is outsourced, the contract organization will be responsible for database quality assurance including, but not limited to, review of data entered into the CRFs by study center personnel for completeness and accuracy and instruction of the study personnel to make any required corrections.

Data management at Indiana University will implement edit checks on the eCRF to enforce data integrity and compliance to the protocol and regulatory requirements. Study center personnel will be responsible for entering study data on the eCRFs. Data management will track eCRFs and review them for completeness, the presence of mandatory

values, consistency, and dated electronic signatures. Queries identified during data discrepancy review will be sent to the study center personnel to be reviewed and resolved in a timely manner.

Adverse Events will be coded using the MedDRA dictionary. Concomitant medications will be coded using the WHO Drug dictionary. Adverse Events and Concomitant Medications will be reviewed for coding consistency and completeness.

At the end of the study, the database will be locked and the data will be released for reporting and statistical analysis.

13 ETHICS/PROTECTION OF HUMAN SUBJECTS

13.1 ETHICAL STANDARD

The Investigator(s) will conduct the study in accordance with this protocol, the guiding principles of the Declaration of Helsinki, ICH GCP guidelines and applicable regulatory requirements.

13.2 INSTITUTIONAL REVIEW BOARD

Before this study starts, the protocol will be submitted to each IEC/IRB for review. As required, the study will not start at a given center before the IEC/IRB for the center provides written approval or a favorable opinion. The IRB will meet all FDA requirements governing IRBs (Code of Federal Regulations, Title 21, Part 56). The IEC will meet local regulations.

13.3 INFORMED CONSENT PROCESS

13.3.1 CONSENT/ASSENT AND OTHER INFORMATIONAL DOCUMENTS PROVIDED TO PARTICIPANTS

Each patient must be provided with a statement that the investigation involves research and that the IRB/EC has approved solicitation of patients to participate; a fair explanation of the procedures to be followed and their purposes, including identification of any procedures which are experimental; a description in lay language of any possible side effects; a description of any attendant discomforts and risks reasonably to be expected; a description of any benefits reasonably to be expected; a disclosure of any appropriate alternative procedures that might be advantageous for the patient; an offer to answer any inquiries concerning the procedures, and instruction that the person is free to withdraw consent and discontinue participation in the project or activity at any time without prejudice to the patient. The informed consent shall include a disclosure that the Investigator is being supported by the NIH to perform the stated research.

13.3.2 CONSENT PROCEDURES AND DOCUMENTATION

A properly executed, written consent in compliance with current U.S. federal code 21CFR part 50, or competent regulatory authority, shall be obtained from each patient prior to entering the study or prior to performing any unusual or non-routine procedure involving risk to the patient.

A patient must give written consent to participate in the study. This consent must be dated and retained by the Principal Investigator as part of the study records. A copy shall be given to the patient. The informed consent process must be documented in the patient's source documents.

Written and/or oral information about the study in a language understandable by the patient will be given to all patients.

13.4 PARTICIPANT AND DATA CONFIDENTIALITY

Each Investigator must assure that the privacy and confidentiality of each study patient's personal identity and personal medical information is maintained at all times. In order to maintain subject privacy and confidentiality, all CRFs, laboratory specimens, evaluation forms, reports, and other records, documents and image material that leave the site

will be identified only by an identification code. This identification code shall on no occasion include study subject's names, initials or date of birth.

Personal medical information may release or review the personal health data of study patients shall take place solely within circumstance, and to third parties, specifically identified by the written informed consent document signed by the study patients, except as permitted by applicable laws and regulations for purposes of monitoring and data verification by the relevant regulatory authorities, the American Heart Association (AHA) and AHA's properly authorized representatives, the quality assurance unit, or regulatory authorities. Personal medical information will always be treated as confidential.

14 DATA HANDLING AND RECORD KEEPING

14.1 DATA COLLECTION AND MANAGEMENT RESPONSIBILITIES

Each Investigator must keep a separate patient identification list showing code numbers, names, and dates of birth to allow unambiguous identification of each patient included in the study. A note will be made in the medical records that the patient is participating in a clinical study.

All required data will be recorded on the CRF by study center personnel according to the data entry guidelines provided by the PI or designee. All CRFs must be kept in good order and updated so they always reflect the latest observations on the patients participating in the study.

When paper CRFs are used, they will be completed legibly in black ink, with reasons given for missing data. Any corrections to the data will be made in a manner that does not obscure the original entry and will be dated and initialed by the Investigator or assigned designee. Each Investigator will sign the statement on the last page of the CRF.

When eCRFs are used, electronic signatures of the Investigator (or designee) will be provided.

Access to the eCRF for data entry and signature is controlled by user identification and password, which are provided by the PI or designee. Study center personnel will be trained, by the PI or designee, in the use of eCRFs and application of electronic signatures before the start of the study.

Because it is extremely important to have proper data collection in a timely manner, the Investigator shall complete the CRFs and on an ongoing basis. If a study monitor is needed and study monitor requests additional data or clarification of data for the CRF, the request must be answered satisfactorily in a timely manner before the next monitoring visit.

14.2 STUDY RECORDS RETENTION

All records related to the study (i.e., source data, source documents, CRFs, copies of protocols and protocol amendments, correspondence, patient identification lists, signed informed consent forms, and other essential documents) must be retained for a minimum of 5 years.

Should an Investigator wish to assign the study records to another party or move them to another location, advance written notice will be given to the PI and AHA.

14.3 PROTOCOL DEVIATIONS

A **protocol deviation** is non-adherence to protocol-specific study procedures or schedules that does not involve inclusion/exclusion criteria, primary objective variable criteria, and/or GCP guidelines. Deviations are considered minor and do not impact the study.

A **protocol violation** is any significant divergence from the protocol, i.e., non-adherence on the part of the patient, the Investigator, or the sponsor to protocol-specific inclusion/exclusion criteria, primary objective variable criteria, and/or GCP guidelines. Protocol violations will be identified and recorded, by study center personnel.

No exceptions to protocol-specific entry criteria will be granted to allow patients to enter a study.

CLINICAL TRIALS.GOV

This study will be registered at the appropriate and required time by the PI, in conjunction with the DCC, to the government-operated clinical trial registry data bank, which contains registration, results, and other information about registered clinical trials at ClinicalTrials.gov. Federal law under FDAAA requires clinical trial information for certain clinical trials to be submitted to the data bank and this study will comply with all reporting requirements for clinical trials.

16 CONFLICT OF INTEREST POLICY

All investigators must adhere to national, regional, and local conflict of interest policies. Prior to publication, all disclosures potentially relevant to this trial will be explicitly stated.

17 ADDITIONAL TRAINING MATERIALS

17.1 LUNG ULTRASOUND TRAINING OVERVIEW

Lung Ultrasound Training Overview

[figure not shown]
Each clinical site already has expertise in LUS (lung ultrasound). However, to minimize variation, a standardized teaching format will be utilized, emphasizing the 8 zone scoring system. Videos perform better to explain LUS and B-lines than a word document or PDF. Videos will be utilized for training purposes, however, a document representation is listed below.

Why use lung ultrasound? For all of the following reasons:

- a. It is fast
- b. No radiation
- c. Non invasive
- d. Repeatable

Ultrasound has been used at the bedside for years. Machines continue to get smaller and smaller and easier to move around.

What is the difference between focused ultrasound and formal echocardiography or radiology studies? Focused ultrasound does not replace formal echocardiography or formal radiology studies. It is meant to answer a binary clinical question. For the purpose of our study, it is meant to guide AHF management. [The figure below with red arrows shows examples of B-lines]

management.

[figure not shown]
Lung (or pulmonary ultrasound) is one of the easiest ultrasound assessments to learn and perform. Even in patients with a high BMI, the lung can be evaluated. Additionally, lung ultrasound has high inter-rater agreement.

In this figure to the left, we are seeing B lines – vertical echogenic artifacts originating from the pleural line, extending to the bottom of the ultrasound screen and moving with lung sliding. In AHF patients, B-line assessment aids in diagnosis, prognosis and may guide acute

Below is the curvilinear probe used for the images.

Below is a pictorial representation of the 8-zone scoring system.

The eight zone protocol breaks each hemi-thorax into 4 zones, divided by the parasternal (PS) Line, Ant axillary line (AAL), posterior axillary line (PAL) and anatomic nipple line (ANL). In the clinical setting of suspected AHF, pulmonary edema is determined sonographically as greater than three B-lines in a rib space in at least two lung zones bilaterally.

[figure not shown]
For scoring purposes, a B line cut off of 10 has been described previously in the literature. This allows for a more precise quantification of pulmonary edema. B lines will be counted as the number seen per acoustic window.

Machine settings

- Enter patient data
- Select **curvilinear** probe
- Select thorax exam
- Set **depth** to 18 cm
- Set **clip length** to 6 seconds
- Turn off tissue harmonics and multi-beam former
- Adjust **gain** so that the rib shadow is black and pleural line is distinct

[figure not shown]
Image acquisition

- Patient supine
- 45 degrees of bed elevation (as possible, if not possible please note on CRF)

[figure not shown]
- Starting off on the **Right** in **Zone 1**: you want the indicator towards the patient's head. Identify ribs by shadowing and identify a rib space (see image below)
- Label R1
- Then turn 90 degrees with **indicator towards patient's right** so you are still in a rib space but the probe is **HORIZONTAL**
- Scan within the zone until you see the area of most B lines
- Record 6 second clip (this should include both inspiration and expiration)
- Repeat the above for Right zones 2-4 and Left zones 1-4
- Obtain **VERTICAL** R4 and L4 zones
- 10 TOTAL videos
- After you leave the bedside, record the number of B lines on a standardized data collection form or in REDCap

COUNTING B LINES

- B lines are vertical echogenic artifacts that originate from the pleural line and extend to the bottom of the ultrasound screen
- Below image is an example of how to count individual B lines

Figure 3: Counting of B-lines using Lung Ultrasound

- In the situation where the whole footprint is 'white out' (see below image) count as 20 B lines
- The maximum number of B lines per sector is 20
- Count the maximum number of B lines you see
- If half of the footprint is a 'white out' count as 10 B lines
- Estimate percentage of white out
- Count up and down from there

PLEURAL EFFUSION

- Document pleural effusion as yes or no
- Note the size (small, medium or large)
- If pleural effusion and no lung is seen in the zone = 0 B lines
- If pleural effusion and lung is seen = count number of B lines seen in lung

For lung ultrasound we rely on the imaging of artifacts to interpret our scans. The main artifact in the lung we see is called reverberation artifact. The physics behind this artifact is briefly explained below.

[figure not shown]
The ultrasound probe is constantly sending ultrasound waves towards whatever tissue is being imaged. When these sound waves get caught between 2 parallel surfaces that are highly reflective, they can bounce around between these highly reflective surfaces and take longer to return to the ultrasound machine.

[figure not shown]
When this happens, you can have an echo that returns to the transducer after a single reflection and this echo will be displayed on the machine in the proper location. Sequential echoes may take longer to return to the transducer, and due to this increase in time the machine thinks that it is from a surface further away so it will appear deeper on the ultrasound image. So what you end up seeing are bright arcs that occur at equidistant intervals.

Below are examples of normal lung, Bat sign, and A lines.

Pleural line and recurrent A lines or reverberation artifact. We see this in normal lung and patients with COPD.

[figure not shown]

The figure below shows B lines. These are vertical echogenic artifacts that originate from the pleural line, extend to the bottom of the ultrasound screen.

[figure not shown]
Normal patients have < 3 B lines per rib space

B lines may be seen outside of AHF. Clinical context is crucial! The table below shows other reasons why B lines may be present.

FOCAL	DIFFUSE
Infarct	Pulmonary Edema
Contusion	ARDS
Cancer	Pulmonary Fibrosis
Pneumonia/Pneumonitis	

Beware if you do NOT see A lines! Below are coalesced B lines. So many B-lines blend together, it could look like normal lung but you note no A lines. (This appears better in video). This is, in fact, diffuse B lines.

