4.2.1 PRIMARY ENDPOINT

The total number of B-lines at the conclusion of ED AHF management

Main Secondary Endpoints:

Dyspnea will also be assessed using a 5-point and 7-point Likert scale.

B-lines ≤ 15 at the conclusion of ED AHF management

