5 STUDY ENROLLMENT AND WITHDRAWAL

5.1 PARTICIPANT INCLUSION CRITERIA

- 1) Age ≥ 21 years
- 2) Presents with shortness of breath at rest or with minimal exertion
- 3) Clinical diagnosis of AHF and presence of > 15 total bilateral B-lines distributed in at least 4 zones on initial LUS
- 4) Hx of chronic HF and any one of the following:
 - i. Chest radiograph consistent with AHF
 - ii. Jugular venous distension
 - iii. Pulmonary rales on auscultation

- iv. Lower extremity edema
- v. BNP > 500pg/mL

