
lines. Half the rib space will be 5. 10 will be the maximum number of B lines per sector.

Image Review

All images will be saved as 6-second video clips. Investigators or study staff will label each clip at the time of scan post-enrollment. For example, Scan 0 is at time of enrollment. Scan 24 is 24 hours post-enrollment, Scan 72 is 72 hours post enrollment. All images will also be date/time stamped, which will be recorded in the local site CRF. Investigators or study staff will fill out a table of their count of B-lines, which will be compared to the Core Lab review. If a rib space is completely whited out with B-lines, this will count as 10 B-lines, half the rib space will count as 5. Importantly, the Core Lab will be blinded to the investigator B-line count.

No PHI will be recorded, only a study ID. Each site will separately and securely store linkages from PHI to the study ID per local IRB approved protocols. Currently, all sites have internal processes to store images for quality control as part of their training programs for fellows and residents. Images will then be transferred to a secure, password protected, access limited server with HIPAA grade security.

Local sites will review images to ensure deidentification. Once de-identified, images will be uploaded to a secure, local server with HIPAA grade security. No post-processing will occur. However, prior to upload to the Core Lab, images will be deliberately mixed with other study patients. This is being done to avoid readers from having 'before and after' images. Images will be then uploaded in batches of 5 patients to a secure, HIPAA grade server.

The Core Lab will then download the images. Importantly, the Core Lab will NOT be a study site to minimize any potential bias or failures of de-identification. Furthermore, the Core Lab will not have access to any clinical information on the patient, further limiting the potential for clinical information to bias image interpretation. To minimize the potential bias of having a single sites images reviewed, images from one site will be mixed with other sites upon arrival at the Core Lab. Reviewers will not see images of patients in chronological order or from only one site at a time.

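### Sections 17.1 and 17.3 score B-lines by different rules (sector maximum 20 versus 10), so the primary endpoint and the 15-line and 7-line figures have no single scale; the analysed reader is also not named

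*Combined protocol and SAP*

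**What the plan says.** Section 4.2.1 defines the primary endpoint as "The total number of B-lines at the conclusion of ED AHF management". Section 17.3 forms that total by adding the counts from eight sectors.

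Two sets of counting instructions follow:

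- **Section 17.1 (counting B-lines):** a fully whited-out footprint scores 20. For half, "If half of the footprint is a 'white out' count as 10 B lines". The cap is explicit: "The maximum number of B lines per sector is 20".
- **Section 17.3 (Core Lab procedure):** "10 will be the maximum number of B lines per sector". The image-review text repeats the rule for a completely whited-out rib space: "this will count as 10 B-lines, half the rib space will count as 5".

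Earlier in Section 17.1 there is also a background remark: "For scoring purposes, a B line cut off of 10 has been described previously in the literature". It adopts no rule for this study.

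Five figures depend on the total:

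- the primary endpoint (4.2.1)
- the entry criterion, "presence of > 15 total bilateral B-lines distributed in at least 4 zones on initial LUS" (5.1)
- the ≤15 threshold, used as a secondary endpoint (4.2.1) and as a condition for ending the protocol (4.1)
- the 15-line difference that Section 10.4.3 treats as significant
- the 7-line planning difference (10.5)

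On readers, Section 17.3 has site personnel count B-lines, and Section 10.6.1 describes the trial as unblinded. Section 4.1 has all images overread by an expert blinded to arm. Section 17.3 keeps the Core Lab readings from investigators until database lock. Neither 4.2.1 nor 10.4.3 says which count is analysed.

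**The concern.** Two readers who each follow the protocol can record different totals for the same clip. That affects eligibility, the ≤15 endpoint and the point at which the protocol ends. It can also reach the Per Protocol Set, because Sections 12 and 14.3 class departures from entry or primary-variable criteria as protocol violations, and Section 10.3 excludes major violations from that set.

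The two rules cannot be read as one for sites and one for the Core Lab. In Section 17.3 the 10/5 rule comes straight after text addressed to site staff ("Investigators or study staff will fill out a table of their count of B-lines"), and those counts are to be compared with the Core Lab's. That comparison needs a common scale.

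The reader question is separate and weaker. Unless the blinded reading is named as the analysed value, a semi-quantitative count made by staff in an unblinded trial could become the primary result.

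**Working it through.** **The plan's own power figure.** Inputs from Section 10.5: 35 per arm, effect size d = 0.7, two-sided α = 0.05, difference of 7 lines. The implied SD is 7/0.7 = 10 lines. For a two-sample t-test, df = 68 and the noncentrality is 0.7 × √(35/2) = 2.93. Power is 0.823, which agrees with the stated 82%. A difference of 14 with an SD of 20 is also d = 0.7 and also gives 0.823. The power statement is therefore correct and free of scale. What lacks a scale is the 7 lines and the SD of 10.

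**The two rules compared.** Apart from the single lines and clear zones, the examples use only scores that both sections define. The second and third rows involve four zones, as the entry criterion requires.

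| Finding | Section 17.1 | Section 17.3 | Figure affected |
|---|---|---|---|
| Maximum over 8 sectors | 8 × 20 = 160 | 8 × 10 = 80 | range of the endpoint |
| One full white-out, one line in each of three other zones | 20 + 3 = 23 | 10 + 3 = 13 | >15 entry rule |
| Two half white-outs, one line in each of two other zones | 2 × 10 + 2 = 22 | 2 × 5 + 2 = 12 | >15 entry rule |
| One full white-out, all other zones clear | 20 | 10 | ≤15 endpoint and protocol end |
| One zone improves from full to half white-out | 20 − 10 = 10 | 10 − 5 = 5 | 7-line planning difference |
| One zone improves from full white-out to clear | 20 | 10 | 15-line difference |

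In every row after the first, the two results fall on opposite sides of the figure named.

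**Where the rules agree.** A sector with 10 or fewer discrete lines and no white-out scores the same under both. They part for white-out and for counts above 10. The ratio between totals therefore varies from scan to scan (23/13 = 1.77; 22/12 = 1.83; 20/10 = 2), and recorded totals cannot be converted by a single multiplier.

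**Sensitivity of the 7-line figure (assumed SDs).** The documents do not say which rule the implied SD of 10 belongs to. If the difference stays at 7 lines and the SD on the rule in force were 7.5, power would be 0.971. If it were 15, power would be 0.486. These SDs are assumptions, one in each direction, and the documents do not show which direction applies.

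**The case against.** The textual conflict itself is hard to dispute. The objections concern its reach.

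- **The divergence is partial.** It arises only with white-out or more than 10 lines in a sector, and the documents do not say how often that occurs. This stands: the examples show that reclassification is possible, not how many patients it would affect.
- **The SD range is artificial.** A change of rule would probably move both the difference and the SD, and joint scaling leaves power at 0.823. This is a fair limit. The range matters only if the 7 lines and the SD came from different rules, and the conclusion does not rest on it.
- **The 10/5 rule may be carried over from another study.** Section 17.2 refers to storage accounts for a differently named study, and the clip labels in 17.3 (24 and 72 hours) match no scheduled scan. This is plausible, but it does not establish which rule was intended.
- **One section speaks of the footprint and the other of the rib space.** The wording differs, but the caps of 20 and 10 are both stated per sector and conflict regardless.
- **Training, clip sign-off and feedback every 10 patients might expose the mismatch.** They might, but only after enrolment had begun, and the feedback would have no agreed rule to refer to.
- **The Core Lab is clearly meant as the analysed reader.** Blinded overreading of all images, and readings that 17.3 calls formal, do point that way. But neither is tied to the primary analysis. A line in the 17.3 training list gives Core Lab review of 20% of clips. It probably concerns training clips, but it should be clarified.

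**Conclusion.** The concern holds and should be corrected before the endpoint is scored for analysis. Two current, unreconciled rules give maxima of 160 and 80, and they can place the same lungs at 23 or 13, on opposite sides of the 15-line threshold. The 7-line and 15-line differences stand for different amounts of congestion under each rule.

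The limits are clear. The 82% power is right for an effect size of 0.7. If one rule is applied to everyone, the between-arm test keeps its type I error. The harm is to the thresholds, to comparability between readers and to interpretation. The number of patients affected cannot be derived from the documents.

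The unnamed reader is a secondary point. The Core Lab reading is implied but not specified, and the main conclusion does not depend on it.

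**What to change.** 1. Reconcile the scoring text in Sections 17.1 and 17.3 to one rule, and use it in the training materials and case report forms. Say whether the literature cut-off of 10 mentioned in 17.1 has any role. Which rule is right is for the sponsor to decide.
2. State that the >15 and ≤15 thresholds, the 15-line difference in 10.4.3, and the 7-line difference with its implied SD of 10 in 10.5 are on that rule. Restate any that came from the other.
3. State in 4.2.1 and 10.4.3 that the primary endpoint is the blinded Core Lab eight-zone total, with site counts used for real-time eligibility and for agreement. Clarify that the 20% review in the training list does not limit the Core Lab's reading of study images.

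The cost is mainly wording. No new scans or readers are needed, because Section 4.1 already plans blinded overreading of all images. Clips already read on the other rule would have to be rescored from the stored videos, since recorded totals cannot be converted.
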